10.3 BOR-confirmation of CR and PR required

BOR is calculated based on the overall visit responses obtained up until objective disease progression (i.e., RECIST response = PD). In the absence of objective disease progression, the BOR is determined using visit responses up until the last evaluable overall visit response.

CR : Overall visit response of CR confirmed at least 4 weeks later by another overall visit response of CR

PR : Overall visit response of PR confirmed at least 4 weeks later by another overall visit response of at least PR (i.e., CR/PR)

SD (≥ 6 weeks): Stable disease recorded at least 6 weeks after the date of first dose (with no prior evidence of progression)

PD: Progression in the absence of CR/PR or SD

NE: Not evaluable.

Overall response first time point	Overall response subsequent time point	Best overall response
CR	CR	CR (if subsequent time point ≥ 4 weeks after first time point)
CR	PR	SD, PD or PR ^a
CR	SD	SD-provided minimum criteria for SD duration are met. Otherwise, PD
CR	PD	SD-provided minimum criteria for SD duration are met. Otherwise, PD
CR	NE	SD-provided minimum criteria for SD duration are met. Otherwise, NE

QMD Ref: CCI	Governing QMD: CCI
Confidentiality Statement	
CCI	

CCI		Sponsor: Theseus Pharmaceuticals, Inc.	
CCI		Protocol Number: THE630-21-101	
STATISTICAL ANALYSIS PLAN. PHASE 2-3-4			

PR	CR	PR
PR	PR	PR (if subsequent time point \geq 4 weeks after first time point)
PR	SD	SD -provided minimum criteria for SD duration are met. Otherwise, PD
PR	PD	SD-provided minimum criteria for SD duration are met. Otherwise, PD
PR	NE	SD-provided minimum criteria for SD duration are met. Otherwise, NE
NE	NE	NE

^aIf a CR is truly met at first time point, then any disease seen at a subsequent time point, even disease meeting PR criteria relative to baseline, makes the disease PD at that point (since disease must have reappeared after CR). Best response would depend on whether minimum duration for SD was met.

Other considerations

There may be cases where a patient has one or more visits that are not evaluable (NE). These visits may fall in between evaluable visits. This should be taken into account. Thus, subsequent timepoint/visit does not literally mean next time point when NE visit may be involved.

[figure not shown]
For example, in a case where a patient had PR, NE, PR then as long as the time between the two visits of PR is at least 4 weeks and there is no evidence of PD between the visits with PR, the patient should be assigned a BOR of PR.

Another example is where a patient has NE, NE, SD, SD, the patient can be assigned a BOR of SD as long as the visits with SD occur at least 6 weeks after first dose.

Lastly, if a patient has only NE visits then BOR of NE.

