##### **5.8.1 Patient Discontinuation**

Patients will be discontinued from further study drug administration in the event of any of the following:

- Intolerable toxicity as determined by the Investigator
- Progression of disease requiring an alternate therapy, in the opinion of Investigator
- Entry into another therapeutic clinical study or start of new anticancer therapy
- Significant deviation from the protocol or eligibility criteria, in the opinion of the medical monitor or Investigator
- Noncompliance with study or follow-up procedures

- Pregnancy
- Patient withdrawal of consent or decision to discontinue participation
- Termination of the study by the Sponsor
- Any other reason that, in the opinion of the Investigator, would justify removal of the patient from the study

In the event that a patient is withdrawn from the study, every effort must be made by the Investigator to document and report the reasons for withdrawal as thoroughly as possible. The reason(s) for withdrawal must be clearly reported on the appropriate page of the patient's eCRF. An eCRF must be completed for any patient enrolled, and an End-of-Treatment reason must be recorded for any patient who is enrolled, regardless of whether they receive study drug.

If a patient is discontinued from the trial for any reason, every effort must be made to perform all End-of-Treatment and 30 Days After Last Dose assessments per the schedule of events. In the event that the patient fails to return for the necessary visit(s), an effort must be made to contact the patient to determine the reason, and this information should be recorded in the appropriate source record and reported as a deviation.

All patients who permanently discontinue the study drug will be followed for survival. For patients who discontinue the study treatment due to a reason other than documented progressive disease (PD), additional tumor assessments should be documented, if available, until disease progression or start of another systemic anti-cancer therapy.

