### 6.3.11 End of Treatment

The End of Treatment visit must be performed within 14 days ( $\pm 7$  days) of the patient's last dose of study drug or the patient/Investigator decision to discontinue study treatment, whichever occurs later.

The following evaluations and procedures will be performed during this visit:

- Vital signs
- ECOG performance status test
- The following procedures must be performed if they were conducted more than 14 days prior to the End of Treatment visit or, if in the opinion of the Investigator, there is reason to believe the results have substantially changed:
  - Physical examination
  - Laboratory assessments: hematology, chemistry (including Troponin T), coagulation, and urinalysis
  - Pregnancy test for FOCP
  - 12-lead ECG (single)
  - Echocardiogram/MUGA scan
- Disease assessment by CT scan and MRI (if more than 4 weeks have passed since the last imaging assessment and progression had not previously been documented)
- THE-630 compliance
- Adverse events assessment
- Recording of concomitant medications
- Blood sample for exploratory biomarkers (at disease progression, only)

- Tissue sample for exploratory biomarker analysis (optional; at disease progression, only)

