4.2.14.1 Best Overall Response (BOR), Confirmed

BOR is defined as the best response achieved at any time point on the study where response refers to the overall response at a given time point (e.g., overall visit response; (derived; see [Appendix 1](#))) according to the following hierarchy:

- Complete Response (CR),
- Partial Response (PR),
- Stable disease (SD)
- Progressive disease (PD)
- Not Evaluable (NE)

per modified RECIST version 1.1 for patients with GIST.

CR or PR responses must be confirmed by repeat imaging at no less than 4 weeks after the date of the initial response (See [Appendix 1](#)). To be assigned SD, patient must have met the SD criteria once after first dose at a minimum of 6 weeks. It should be noted that patients with no measurable disease at baseline should have overall visit response(s) of Non-CR/Non-PD. In these cases, for analysis purposes, BOR will be set to NE. Additionally, if a patient does not have any post-baseline overall visit response assessments, then the patient will be assigned BOR of NE.

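### The SAP's response window closes at progression but not at new systemic anticancer therapy, so an End-of-Treatment scan taken after a switch can count towards THE-630

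*SAP*

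**What the plan says.** SAP 4.2.14.1 sets the frame: "BOR is defined as the best response achieved at any time point on the study". The wording is on study, not on treatment. SAP 10.3 then gives the data window. With progression, "BOR is calculated based on the overall visit responses obtained up until objective disease progression". Without it, "In the absence of objective disease progression, the BOR is determined using visit responses up until the last evaluable overall visit response". The confirmation rule for a partial response (PR) is "Overall visit response of PR confirmed at least 4 weeks later by another overall visit response of at least PR". Stable disease (SD) needs a scan at least 6 weeks after first dose with no earlier progression. Neither rule refers to treatment status.

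Confirmed ORR (4.2.14.2) and DCR (4.2.14.4) follow from these visit responses. CBR at 16 weeks (4.2.14.3) looks at progression and scan timing only. Best percentage change (4.2.14.5) has no cut at new therapy either. Nor do protocol 9.3.4 and 9.5.

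One sentence in the protocol does stop at new therapy. Section 5.8.1 says that, for patients who stop for a reason other than progression, "additional tumor assessments should be documented, if available, until disease progression or start of another systemic anti-cancer therapy". The same section lists as a reason to stop study drug "Entry into another therapeutic clinical study or start of new anticancer therapy", and asks for every effort to complete the End-of-Treatment assessments whatever the reason. Section 6.3.11 makes the End-of-Treatment scan due "if more than 4 weeks have passed since the last imaging assessment and progression had not previously been documented". It does not exclude a patient who has already started another drug.

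**The concern.** A scan taken after the next anticancer drug has started reflects both treatments. If it enters the response derivation, disease control or persistence of a response that may owe something to the second drug is credited to THE-630. The protocol's own instruction in 5.8.1 suggests that such scans are not wanted, but the SAP does not carry that limit into the analysis.

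ORR, DCR and CBR are the efficacy rates that remain in SAP version 3.0. Its revision history drops PFS, OS and the listings that are not numbered as tables. SAP 4.9 leaves concomitant medications unreported, and no new-therapy marker is specified for the swimmer plot. A reader of the report would have little means of seeing that a counted scan came after a switch.

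**Working it through.** The plan states no figure for this point, so the check is whether the timing rules allow it, which way it biases, and what one patient is worth.

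**Inputs**
- End-of-Treatment visit: 14 ± 7 days after last dose or stop decision, whichever is later (protocol 6.3.11). The window is 7 to 21 days.
- End-of-Treatment scan: due if more than 28 days have passed since the last scan and no progression is documented (protocol 6.3.11).
- Scheduled scans: Day 28 ± 3 of even cycles (protocol 7.2.1), so about Days 56 and 112.
- SD: at least 6 weeks after first dose (SAP 10.3). With first dose on Day 1, this is Day 1 + 42 = Day 43.
- PR confirmation: at least 28 days (SAP 10.3).
- CBR: at least 109 days (SAP 4.2.14.3), which agrees with 4 × 28 − 3 = 109.
- Patients: 32 enrolled (SAP 1), all assumed dosed and in the Full Analysis Set.

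**1. Stable disease.** Last dose Day 30, next drug Day 37, scan Day 44 reads SD. The visit window is Days 37 to 51. The scan is 44 − 1 = 43 days after first dose, past 42. The baseline scan is more than 4 weeks old, so the scan is due, and the first scheduled scan has not been reached. BOR is SD and DCR counts it. With a cut at new therapy there is no post-baseline scan, so BOR is not evaluable. The earliest last dose for which this works is Day 43 − 21 = Day 22.

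**2. Confirmation of a PR.** PR on Day 56, last dose Day 80, next drug Day 85, scan Day 94 reads PR. The visit window is Days 87 to 101. The gap is 94 − 56 = 38 days, at least 28, so the PR is confirmed. More generally, the scan is due only when more than 28 days have passed, so any due scan after a first PR on the last scan meets the confirmation interval. The earliest such scan is Day 56 + 29 = Day 85, with last dose from Day 85 − 21 = Day 64. With the cut, the PR is unconfirmed and ORR loses it. DCR does not, because Day 56 is past the SD minimum.

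**3. CBR.** SD on Day 56, last dose Day 90, next drug Day 100, scan Day 110 reads SD. The visit window is Days 97 to 111, and 110 − 56 = 54 days makes the scan due. The 109-day rule is met. With the cut there is no scan at Week 16 or later, so the patient does not count. The earliest last dose is Day 109 − 21 = Day 88, or Day 89 if 109 is counted as elapsed days.

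**4. Direction.** A scan after the switch can add SD, a confirmation or a CBR success. If it shows progression, it does not remove SD or a confirmed response already earned. For ORR, DCR and CBR the bias is therefore upward or nil. For best percentage change, a later scan can only deepen the value of a patient who already has one. It can also add a value, in either direction, for a patient who has none.

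**5. Size of one patient** (assumed counts, exact 95% intervals)

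| Denominator | None counted | One counted | Shift |
|---|---|---|---|
| 32, overall | 0% (0 to 10.9) | 3.1% (0.1 to 16.2) | 3.1 points |
| 6, dose cohort | 0% (0 to 45.9) | 16.7% (0.4 to 64.1) | 16.7 points |
| 3, dose cohort | 0% (0 to 70.8) | 33.3% (0.8 to 90.6) | 33.3 points |

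If 0 to 3 patients were affected, which is an assumption, an overall rate would move by 0 to 3/32 = 9.4 points. A dose level with backfill moves less; at 20 patients, for example, one patient is 1/20 = 5.0 points.

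**The case against.** The strongest case is that the protocol already prevents this. Section 5.8.1 stops documentation at new systemic therapy, and an End-of-Treatment scan could itself be read as one of those assessments. Table 7 bars other systemic anticancer therapy during the treatment period, and 6.3.11 sits under the Treatment Period heading, so a new drug before that visit would arguably be a deviation. Both points make the situation uncommon. Neither settles it. The 5.8.1 sentence is a collection instruction about additional scans, whereas the End-of-Treatment scan is scheduled separately. Section 5.8.1 also foresees patients who stop because they start another therapy and still wants their End-of-Treatment assessments. The Table 7 ban governs conduct, not which scans the SAP analyses.

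A second argument is that little depends on it. Phase 2 will not be initiated, Phase 1 efficacy is secondary and no comparisons are planned. The SAP wording on BOR also follows protocol 9.3.4. This stands, and it is why the point is minor.

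Third, SAP version 3.0 refers to version 1.0 for original details, and version 1.0 is not available here. A new-therapy rule there cannot be excluded, but the current text contains none.

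A reader might infer that a patient who stops because of new therapy is necessarily scanned on the new drug. The documents do not say so: the visit is timed from last dose or the decision to stop, and the scan can come before the switch. No scan is due if one was done in the previous 4 weeks.

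**Conclusion.** The gap is real and narrow. As written, the SAP lets an End-of-Treatment scan taken after the start of another systemic therapy count for BOR, ORR, DCR, CBR and best percentage change, and for the rates the bias can only be upward. It needs a patient who stops without progression, starts the next drug before the visit, and is due a scan. The number of such patients is not in the documents and may be zero. Each shifts an overall rate by 3.1 points, assuming all 32 are in the Full Analysis Set. The 17 to 33 point shift within a dose level holds only for 3 to 6 patients.

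Two stronger readings should be avoided. One is that the excess would concentrate at higher doses because of toxicity; discontinuation reasons by dose are not given, and 5.8.1 lists several others, including consent withdrawal and sponsor termination. The other is that responses achieved on another drug are being reported. In the PR example the response arose on THE-630 and the second scan is 9 days into the next drug, which shows possible contamination of persistence and no more.

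**What to change.** In SAP 4.2.14.1 to 4.2.14.5 and 10.3, state that only tumor assessments dated on or before the earlier of first progression and the start of the first subsequent systemic anticancer therapy are used. Section 4.2.14.1 must be included, or its any-time-point definition will contradict the rule. This brings the analysis into line with protocol 5.8.1.

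First confirm that the eCRF captures the start date: protocol 6.4.2 requires new therapies to be reported but does not name a date. Add a partial-date rule, since SAP 4.2.5 to 4.2.8 have none for subsequent therapy and a month-only date cannot be placed reliably within a window of about 3 weeks. Keep later scans in the swimmer plot, marked as post-therapy, and report how many patients the cut affects, including if that number is zero.

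The cost is a short SAP addition, one date condition in the response dataset, the partial-date rule and the eCRF check. Point estimates may become slightly less favourable.

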11 APPENDIX 3: SAS CODE

11.1 ORR

QMD Ref: CCI	Governing QMD: CCI
Confidentiality Statement	
CCI	

CCI		Sponsor: Theseus Pharmaceuticals, Inc.	
CCI		Protocol Number: THE630-21-101	
STATISTICAL ANALYSIS PLAN. PHASE 2-3-4			

12 APPENDIX 4: LABORATORY TESTS

12.1 Select Laboratory Parameters-CTCAE Grades

The following lab parameters will have CTCAE grades assigned based on numeric criteria listed for CTCAE v5.0 or v4.03. It should be noted that several parameters may have different set of grades based on the CTCAE term of interest (e.g., Sodium (decreased [CTCAE term: hyponatremia] and increased [CTCAE term: hypernatremia]), These CTCAE terms will be summarized separately.

Grades will be derived based on numeric criteria listed in CTCAE v5.0 (or v4.03 in cases where categorization for a laboratory assessment based on numerical value was not possible using CTCAE v5.0) and will not take into consideration clinical signs or symptoms. The below table lists numeric criteria used to determine a grade for a given a parameter value in this study. Note, a semi-colon indicates ‘or’ within the description of the grade.

Hematology

Parameter	CTCAE Term	Directionality	Grade 1	Grade 2	Grade 3	Grade 4
Hemoglobin	Anemia	Decrease	Hemoglobin(Hgb) <LLN-10.0 g/dL; <LLN-6.2 mmol/L; <LLN-100 g/L	Hgb <10.0-8.0 g/dL; <6.2-4.9 mmol/L; <100-80g/L	Hgb <8.0 g/dL; <4.9 mmol/L; <80g/L	N/A
White Blood Cells (WBC)	White Blood Cell Decreased	Decrease	<LLN-3000/mm3; <LLN-3.0 x 10e9/L	<3000-2000/mm3; <3.0-2.0 x 10e9/L	<2000-1000/mm3; <2.0-1.0 x 10e9/L	<1000/mm3; <1.0 x 10e9/L

QMD Ref: CCI	Governing QMD: CCI
Confidentiality Statement	
CCI	

CCI		Sponsor: Theseus Pharmaceuticals, Inc.	
CCI		Protocol Number: THE630-21-101	
STATISTICAL ANALYSIS PLAN. PHASE 2-3-4			

Parameter	CTCAE Term	Directionality	Grade 1	Grade 2	Grade 3	Grade 4
Platelet count	Platelet Count Decreased	Decrease	<LLN-75,000/mm ³ ; <LLN-75.0 x 10 ⁹ /L	<75,000-50,000/mm ³ ; <75.0-50.0 x 10 ⁹ /L	<50,000-25,000/mm ³ ; <50.0-25.0 x 10 ⁹ /L	<25,000/mm ³ ; <25.0 x 10 ⁹ /L
Neutrophil count (absolute)	Neutrophil Count Decreased	Decrease	<LLN-1500/mm ³ ; <LLN-1.5 x 10 ⁹ /L	<1500-1000/mm ³ ; <1.5-1.0 x 10 ⁹ /L	<1000-500/mm ³ ; <1.0-0.5 x 10 ⁹ /L	<500/mm ³ ; <0.5 x 10 ⁹ /L
Lymphocyte count (absolute)	Lymphocyte Count Decreased	Decrease	<LLN - 800/mm ³ ; <LLN - 0.8 x 10 ⁹ /L	<800 - 500/mm ³ ; <0.8 - 0.5 x 10 ⁹ /L	<500 - 200/mm ³ ; <0.5 - 0.2 x 10 ⁹ /L	<200/mm ³ ; <0.2 x 10 ⁹ /L

ULN=Upper limit of normal

Values in table are based on CTCAE v5.0.

Chemistry

Parameter	CTCAE Term	Directionality	Grade 1	Grade 2	Grade 3	Grade 4
Sodium	Hyponatremia	Decrease	<LLN-130 mmol/L	125-129 mmol/L	120-124 mmol/L	<120 mmol/L
Sodium	Hypernatremia	Increase	>ULN-150 mmol/L	>150-155 mmol/L	>155-160 mmol/L	>160 mmol/L

QMD Ref: CCI	Governing QMD: CCI
Confidentiality Statement	
CCI	

CCI		Sponsor: Theseus Pharmaceuticals, Inc.	
CCI		Protocol Number: THE630-21-101	
STATISTICAL ANALYSIS PLAN. PHASE 2-3-4			

Parameter	CTCAE Term	Directionality	Grade 1	Grade 2	Grade 3	Grade 4
Potassium	Hypokalemia	Decrease	<LLN-3.0 mmol/L	N/A (for purpose of this study)	<3.0-2.5 mmol/L	<2.5 mmol/L
Magnesium	Hypomagnesemia	Decrease	<LLN-1.2 mg/dL; <LLN-0.5 mmol/L	<1.2-0.9 mg/dL; <0.5-0.4 mmol/L	<0.9-0.7 mg/dL; <0.4-0.3 mmol/L	<0.7 mg/dL; <0.3 mmol/L
Magnesium	Hypermagnesemia	Increase	>ULN-3.0 mg/dL; >ULN-1.23 mmol/L	>3.0-8.0 mg/dL; >1.23-3.30 mmol/L	>8.0 mg/dL; >3.30 mmol/L	N/A
Phosphorous (based on CTCAE v4.03 criteria)	Hypophosphatemia	Decrease	<LLN - 2.5 mg/dL; <LLN - 0.8 mmol/L	<2.5 - 2.0 mg/dL; <0.8 - 0.6 mmol/L	<2.0 - 1.0 mg/dL; <0.6 - 0.3 mmol/L	<1.0 mg/dL; <0.3 mmol/L
Calcium (Total) (correct calcium numeric criteria will be applied)	Hypocalcemia	Decrease	Corrected serum calcium of <LLN-8.0 mg/dL; <LLN-2.0 mmol/L	Corrected serum calcium of <8.0-7.0 mg/dL; <2.0-1.75 mmol/L	Corrected serum calcium of <7.0-6.0 mg/dL; <1.75-1.5 mmol/L	Corrected serum calcium of <6.0 mg/dL; <1.5 mmol/L

QMD Ref: CCI	Governing QMD: CCI
Confidentiality Statement	
CCI	

CCI		Sponsor: Theseus Pharmaceuticals, Inc.	
CCI		Protocol Number: THE630-21-101	
STATISTICAL ANALYSIS PLAN. PHASE 2-3-4			

Parameter	CTCAE Term	Directionality	Grade 1	Grade 2	Grade 3	Grade 4
Calcium Total (correct calcium numeric criteria will be applied)	Hypercalcemia	Increase	Corrected serum calcium of >ULN-11.5 mg/dL; >ULN-2.9 mmol/L	Corrected serum calcium of >11.5-12.5 mg/dL; >2.9-3.1 mmol/L	Corrected serum calcium of >12.5-13.5 mg/dL; >3.1-3.4 mmol/L	Corrected serum calcium of >13.5 mg/dL; >3.4 mmol/L
ALT	Alanine Aminotransferase Increased	Increase	>ULN-3.0 x ULN if baseline was normal; 1.5-3.0 x baseline if baseline was high abnormal (> ULN)	>3.0-5.0 x ULN if baseline was normal; >3.0-5.0 x baseline if baseline was high abnormal (> ULN)	>5.0-20.0 x ULN if baseline was normal; >5.0-20.0 x baseline if baseline was high abnormal (> ULN)	>20.0 x ULN if baseline was normal; >20.0 x baseline if baseline was high abnormal (> ULN)
AST	Aspartate Aminotransferase Increased	Increase	>ULN-3.0xULN if baseline was normal; 1.5-3.0x baseline if baseline was high abnormal (i.e., > ULN)	>3.0-5.0xULN if baseline was normal; >3.0-5.0x baseline if baseline was high abnormal (i.e., > ULN)	>5.0-20.0xULN if baseline was normal; >5.0-20.0x baseline if baseline was high abnormal (i.e., > ULN)	>20.0xULN if baseline was normal; >20.0x baseline if baseline was abnormal high abnormal (i.e., > ULN)
Total bilirubin	Blood Bilirubin Increased	Increase	>ULN-1.5 x ULN if baseline was normal; > 1.0-1.5 x baseline if baseline was high abnormal (i.e., > ULN)	>1.5-3.0 x ULN if baseline was normal; >1.5-3.0 x baseline if baseline was high abnormal (i.e., > ULN)	>3.0-10.0 x ULN if baseline was normal; >3.0-10.0 x baseline if baseline was high abnormal (i.e., > ULN)	>10.0 x ULN if baseline was normal; >10.0 x baseline if baseline was high abnormal (i.e., > ULN)
Albumin	Hypoalbuminemia	Decrease	<LLN-3 g/dL; <LLN-30 g/L	<3-2 g/dL; <30-20 g/L	<2 g/dL; <20 g/L	
Creatinine	Creatinine Increased	Increase	>ULN-1.5 x ULN	>1.5-3.0 x baseline; >1.5-3.0 x ULN	>3.0 x baseline; >3.0-6.0 x ULN	>6.0 x ULN

QMD Ref: CCI	Governing QMD: CCI
Confidentiality Statement	
CCI	

CCI		
CCI	Sponsor:	Theseus Pharmaceuticals, Inc.
	Protocol Number:	THE630-21-101
STATISTICAL ANALYSIS PLAN. PHASE 2-3-4		

Parameter	CTCAE Term	Directionality	Grade 1	Grade 2	Grade 3	Grade 4
Amylase (based on CTCAE v4.03 criteria)	Serum Amylase Increased	Increase	>ULN-1.5 x ULN	>1.5-2.0 x ULN;	>2.0-5.0 x ULN	>5.0 x ULN
Lipase (based on CTCAE v4.03 criteria)	Lipase Increased	Increase	>ULN-1.5 x ULN	>1.5-2.0 x ULN	>2.0-5.0 x ULN	>5.0 x ULN
CK (Creatinine Kinase)	CPK Increased	Increase	>ULN-2.5 x ULN	>2.5 x ULN-5 x ULN	>5 x ULN-10 x ULN	>10 x ULN
Alkaline phosphatase	Alkaline Phosphatase increased	Increase	>ULN-2.5xULN if baseline was normal; 2.0-2.5x baseline if baseline was high abnormal (i.e., > ULN)	>2.5-5.0xULN if baseline was normal; >2.5-5.0x baseline if baseline was high abnormal (i.e., > ULN)	>5.0-20.0xULN if baseline was normal; >5.0-20.0x baseline if baseline was high abnormal (i.e., > ULN)	>20.0xULN if baseline was normal; >20.0x baseline if baseline was high abnormal (i.e., > ULN)
Alkaline phosphatase	Alkaline Phosphatase increased	Increase	>ULN-2.5xULN if baseline was normal; 2.0-2.5x baseline if baseline was high abnormal (i.e., > ULN)	>2.5-5.0xULN if baseline was normal; >2.5-5.0x baseline if baseline was high abnormal (i.e., > ULN)	>5.0-20.0xULN if baseline was normal; >5.0-20.0x baseline if baseline was high abnormal (i.e., > ULN)	>20.0xULN if baseline was normal; >20.0x baseline if baseline was high abnormal (i.e., > ULN)
Glucose (based on CTCAE v4.03 criteria)	Hyperglycemia	Increase	glucose value >ULN - 160 mg/dL; glucose value >ULN - 8.9 mmol/L	glucose value >160 - 250 mg/dL; glucose value >8.9 - 13.9 mmol/L	>250 - 500 mg/dL; >13.9 - 27.8 mmol/L	>500 mg/dL; >27.8 mmol/L
Glucose	Hypoglycemia	Decrease	<LLN-55 mg/dL; <LLN-3.0 mmol/L	<55-40 mg/dL; <3.0-2.2 mmol/L	<40-30 mg/dL; <2.2-1.7 mmol/L	<30 mg/dL; <1.7 mmol/L

QMD Ref: CCI	Governing QMD: CCI
Confidentiality Statement	
CCI	

CCI		CCI	
CCI		Sponsor:	Theseus Pharmaceuticals, Inc.
		Protocol Number:	THE630-21-101
STATISTICAL ANALYSIS PLAN. PHASE 2-3-4			

QMD Ref: CCI	Governing QMD: CCI
Confidentiality Statement	
CCI	

REF: CCI

CCI		Sponsor: Theseus Pharmaceuticals, Inc.	
CCI		Protocol Number: THE630-21-101	
STATISTICAL ANALYSIS PLAN. PHASE 2-3-4			

Coagulation

Parameter	CTCAE Term	Directionality	Grade 1	Grade 2	Grade 3	Grade 4
INR	INR Increased	Increase	>1.2-1.5; >1-1.5 x baseline if on anticoagulation**	>1.5-2.5; >1.5-2.5 x baseline if on anticoagulation**	>2.5; >2.5 x baseline if on anticoagulation**	
aPTT	Activated Partial Thromboplastin time prolonged	Increase	>ULN-1.5 x ULN	>1.5-2.5 x ULN	>2.5 x ULN	

**A subject who is taking a medication assigned WHODrug ATC3 level code “B01A” (antithrombotic agents) will be considered to be on an anticoagulation.

QMD Ref: CCI	Governing QMD: CCI
Confidentiality Statement	
CCI	

CCI			
CCI		Sponsor:	Theseus Pharmaceuticals, Inc.
		Protocol Number:	THE630-21-101
STATISTICAL ANALYSIS PLAN. PHASE 2-3-4			

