4.15.2 Laboratory Data

QMD Ref: CCI	Governing QMD: CCI
Confidentiality Statement	
CCI	

CCI		Sponsor: Theseus Pharmaceuticals, Inc.	
CCI		Protocol Number: THE630-21-101	
STATISTICAL ANALYSIS PLAN. PHASE 2-3-4			

Laboratory samples will be analyzed by local laboratories. For reporting purposes, lab parameters will be reported using SI units.

Each measurement (continuous data) will be classed as below, within, or above normal range, based on ranges supplied by the laboratory used. To identify laboratory values of potential clinical importance, National Cancer Institute Common Terminology Criteria for Adverse Events (CTCAE) will be used to assign grades for select laboratory parameters where applicable (See [Appendix 4](#)). A shift table representing two-way frequency tabulation for baseline and the worst post-baseline value according to the CTCAE grade, by cohort and overall, will be provided. For analysis purpose, patients with a lab parameter value that does not meet CTCAE criteria (e.g., value is within normal range) at baseline or any time post-baseline, will be assigned a Grade of 0 for said visit.

The incidence of patients meeting Hy’s law criteria will be summarized for any time, post-baseline (See [Appendix 5](#)).

A listing of any abnormal laboratory measurements recorded throughout the study will be presented.

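### SAP Appendix 4 grades potassium only downward, so the chemistry shift table has no graded display of raised potassium by dose level

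*SAP*

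**What the plan says.** SAP 4.15.2 assigns CTCAE grades to selected laboratory parameters and tabulates baseline grade against worst post-baseline grade, by cohort and overall. A visit with "a lab parameter value that does not meet CTCAE criteria (e.g., value is within normal range") is set to Grade 0.

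SAP 12.1 supplies the grading rules: "The below table lists numeric criteria used to determine a grade for a given a parameter value in this study". It foresees parameters with a low and a high term, giving as its example "Sodium (decreased [CTCAE term: hyponatremia] and increased [CTCAE term: hypernatremia"]), and adds: "These CTCAE terms will be summarized separately".

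In the chemistry part of that table:
- Potassium has one row, "Potassium Hypokalemia Decrease". Its Grade 2 cell is "N/A (for purpose of this study"), which concerns low potassium only.
- High-direction rows do exist for other analytes, for example "Sodium Hypernatremia Increase" and "Magnesium Hypermagnesemia Increase". Calcium and glucose also have both directions.

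SAP section 9 lists the laboratory displays: a listing of abnormal values (14.3.4.1), grade-shift tables for hematology, chemistry and coagulation (14.3.4.2 to 14.3.4.4), and a table and a listing based on Hy's law (14.3.4.5 and 14.3.4.6).

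**The concern.** Potassium is part of the required chemistry panel (Protocol Table 8), so the data exist. The SAP states the principle of grading both directions and applies it to four other analytes, but potassium is graded only for low values, with no explanation. This looks like an omission.

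The stake is the laboratory safety summary. The Phase 1 primary endpoint is the safety profile, this is a first-in-human trial, and the DLT definition itself mentions electrolyte disturbances. Protocol 9.6 planned descriptive statistics of laboratory changes over time. The SAP revision history records that descriptive laboratory summaries and grade-increase tables were dropped after termination, and section 9 no longer contains them. The shift tables therefore carry nearly all of the laboratory-derived summary, and a missing direction weighs more than it would have under the fuller plan.

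**Working it through.** No figure in the plan needs reproducing. The check is a row-by-row reading of Appendix 4, followed by applying its rule to raised values.

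**Step 1: directions graded, electrolytes and glucose (SAP 12.1).**

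| Parameter | Low row | High row |
|---|---|---|
| Sodium | yes | yes |
| Potassium | yes | no |
| Magnesium | yes | yes |
| Phosphorous | yes | no |
| Calcium | yes | yes |
| Glucose | yes | yes |

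Four of these six are graded both ways. Potassium and phosphorous are graded downward only.

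**Step 2: potassium criteria as listed.** Grade 1 runs from below LLN down to 3.0 mmol/L, Grade 2 is not used, Grade 3 is below 3.0 down to 2.5, and Grade 4 is below 2.5. Every criterion requires a value below LLN.

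**Step 3: apply the rule.** The potassium values here are illustrative assumptions, with an assumed ULN near 5 mmol/L. The result does not depend on that ULN, because any value above normal fails every criterion in step 2.

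| Value | Criterion met | Grade |
|---|---|---|
| Potassium 5.6 mmol/L | none | 0 |
| Potassium 6.5 mmol/L | none | 0 |
| Potassium 7.5 mmol/L | none | 0 |
| Sodium 152 mmol/L | hypernatremia, >150 to 155 | 2 |
| Magnesium 3.5 mmol/L | hypermagnesemia, >3.30 | 3 |

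A patient who goes from normal potassium to any of the three raised values, with no low value, sits in the Grade 0 to Grade 0 cell of the potassium panel in Table 14.3.4.3. A patient who also had a low value shows that hypokalemia grade; the high value is still not displayed.

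**Step 4: look for another laboratory table.**
- Hematology and coagulation shifts: potassium is not included.
- Hy's law displays (Appendix 5): these use ALT, AST, bilirubin, ALP and INR, not potassium.
- The below, within or above range classification in SAP 4.15.2: no table in section 9 tabulates it.
- Listing 14.3.4.1: raised potassium would appear here as individual lines, not as counts by grade.

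**Step 5: could the row have been lost in text extraction?** Sodium, magnesium and calcium list the low row first, so a hyperkalemia row would be expected directly after hypokalemia. That position holds hypomagnesemia. Glucose lists the high row first, and a page break falls just before the potassium row, so loss cannot be fully excluded, but nothing points to it.

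**The case against.** The strongest reply is that a raised potassium still has routes into the report. Investigators judge each out-of-range value for clinical significance (Protocol 7.3.4). A clinically relevant change can be an adverse event (Protocol 8.2.5), and it is then CTCAE-graded and tabulated by cohort, preferred term and maximum grade (SAP 4.15.1). Listing 14.3.4.1 is sorted by cohort (SAP 4.3) and is readable with 32 enrolled patients. This stands. A reader might infer that raised potassium would be invisible at every dose level, and the documents do not support that. What is missing is the laboratory-derived count, which matters mainly for values the investigator did not report as events.

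A reader might also infer that Grade 0 misclassifies these patients. It does not: because terms are summarised separately, Grade 0 for hypokalemia is correct for a high value, just as a hypernatremic patient is Grade 0 for hyponatremia. The fault is an absent display. Nor does the not-applicable cell declare high potassium out of scope; it belongs to the hypokalemia row.

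Finally, the appendix covers selected parameters, phosphorous is also graded downward only, and all five hematology rows are one-directional. The SAP therefore never promises both directions for everything, and potassium is not unique. That tempers the point but gives no reason for treating potassium differently from sodium, magnesium and calcium.

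**Conclusion.** The concern holds as a gap in the laboratory-derived safety summary. Appendix 4 gives no raised potassium value a grade above 0, and no planned laboratory table counts such values by grade and dose level.

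Its reach is every above-normal potassium value in the Full Analysis Set, that is, the dosed patients among the 32 enrolled. How many patients that affects cannot be determined from the documents. DLTs are identified from flagged adverse events, so DLT and MTD determination do not change, and neither does any efficacy analysis.

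The conclusion assumes that the extracted Appendix 4 is complete. It is a worthwhile, low-cost correction to a descriptive table in a trial whose primary endpoint is safety.

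**What to change.** Add a row to the chemistry part of Appendix 4: Potassium, Hyperkalemia, Increase. Take the numeric cut-offs from CTCAE under the version rule already in SAP 12.1 (v5.0, or v4.03 where v5.0 does not allow grading on a numeric value alone); the documents do not print them. Summarise the term separately from hypokalemia in Table 14.3.4.3, as is done for sodium.

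If the one-directional choice is deliberate, say so in the SAP and footnote the table so that Grade 0 is not read as normal potassium.

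The data are already collected. The cost is one appendix row, a small programming change, validation of the revised table by the independent programming that section 9 assigns to it, and a documented update to the signed SAP version 3.0.
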